4.1 Primary Efficacy Variable

The primary efficacy assessment for this study is based on the time to climb 4 standard stairs (4SC) at 18 months. The primary endpoint is the mean change in time to climb 4 standard stairs before and after 18 months of treatment of givinostat versus placebo. Baseline 4SC will be the measurement taken at the randomisation assessment unless this is missing in which case baseline will be taken as the last non-missing value recorded prior to or on the date of first study treatment.

In addition to the 4SC recorded in seconds, functional adaptation employed by the subject during the test will be evaluated and graded by functional evaluators according to standardised scales (See Appendix 7.1).

Summary statistics of 4SC observed values and change from baseline will be presented by visit and treatment. In addition, a plot of the average 4SC at each visit will be produced by treatment group.

A shift table showing the movement of subjects with respect to functional adaptation options for the 4SC from baseline to 18 months after treatment will be presented by treatment.

Furthermore, in order to additionally assess the 4SC data in terms of velocity rather than time, a reciprocal transformation will be applied to convert the timed results to appropriate units of velocity, according to the following conversion:

$$\text{Velocity (stairs/second)} = 4 / \text{Completion time (seconds)}$$

where this conversion is applied following any imputation of missing data as described in Section 4.4.4. The summary statistics and plot described above will be repeated for these transformed values. Analysis of this endpoint (described in Section 4.4.2) will also be repeated on the transformed scale.

All 4SC and functional adaptation data will be listed.

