The need for a possible log transformation of these variables will be investigated prior to unblinding by assessing the ANCOVA model residuals without a treatment term. Where data are transformed for analysis, back transformation will be applied for the presentation of results. Presentation of the tables will be amended as needed for this, for example with the addition of an explanatory footnote.

Analysis of cumulative loss of function on the NSAA over 18 months of treatment with givinostat or placebo will be performed using negative binomial regression. The dependent variable will be the subject cumulative number of failures across all post-baseline visits. Total failed items at baseline, baseline values for: 4SC, time to rise from floor, time to run/walk 10 metres, distance walked in 6 minutes and re-derived age at first dose (in years and months) will be included as independent covariates in the model, with randomised treatment group and concomitant steroid use included as independent classification factors. The estimated cumulative number of failures across 18 months and associated 2-sided CIs from the model will be presented for each treatment group. The treatment effect will be presented as the ratio of cumulative failures for givinostat relative to placebo along with the associated 2-sided CI and p-value, where a lower ratio indicates a greater reduction in cumulative number of failures across 18 months for givinostat compared with placebo.

The binary efficacy variables (proportion of subjects with $\geq 10\%$ persistent worsening in 6MWT, proportion of subjects losing ambulation during the study) will be analysed using logistic regression. In each instance baseline values for: 4SC, time to rise from floor, time to run/walk 10 metres, distance walked in 6 minutes and re-derived age at first dose (in years and months), will be included as independent covariates. Randomised treatment group and concomitant steroid use will be included as independent classification factors. The odds ratio comparing the treatment groups will be presented, together with its associated 2-sided CI and p-value.

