4.4.4 Handling of Missing Data

4.4.4.1 Classification and Imputation

For the efficacy analyses, any missing data for continuous values for a subject will be classified as follows:

1. the subject has missing data due to reasons other than being non-ambulatory or physically unable to perform the test / assessment
2. the subject has missing data due to being either non-ambulatory or otherwise physically unable to perform the test / assessment.

Any missing values classified as 1 will be imputed using the mean of all non-missing values for the respective measurement and timepoint across all subjects randomised to the respective treatment and in the respective concomitant steroid stratum and Group (i.e. Group A, target population or Group B, off-target population).

Any missing values classified as 2 will be imputed by setting the value to zero or to twice the maximum non-missing value recorded across all subjects depending on the directionality of the test.

In all cases, imputation of any data classified as 1 will be completed first, followed by imputation of any data classified as 2.

Classification and imputation of missing data will be completed prior to any transformation of the data for analysis. For example transformation of the timed function test results for presentation of velocity or any log transformation applied as needed (per Section 4.4.2).

For binary or time to event variables where missing data means that the binary response or time to event cannot be determined, the missing data from which the variable is derived (e.g. 6MWT values) will first be classified and imputed, as described above, in order to then derive the binary response or the time to event. Exceptions to this are where the criteria for deriving the binary response themselves refer to presence of missing data, for example loss of ambulation. The classification described above will be used for the relevant missing data in these cases in order to confirm physical inability to complete the respective test. Further details are given below regarding the rules for derivation of the binary endpoints in the presence of missing data.

For the NSAA assessment, where the total score is a sum of ordinal item scores, imputation of Class 1 and Class 2 data will follow a different approach as defined in Appendix 7.5.4.

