Class 2: $x_{ijk} = 2 \times \text{Max}(x)$ where $\text{Max}(x)$ is the maximum non-missing value recorded for the variable across all subjects, regardless of treatment, stratum or Group.

Following the assignment of imputed values, the data x_{ijk} will be analysed as described in Section 4.4.2 and Sections 4.1 to 4.3.10, as relevant to the respective variable using PROC MIXED, ensuring that reference levels are stated for all class variables so that difference in LSmeans is calculated as givinostat-placebo. F-tests from PROC MIXED will be based on Kenward-Roger's adjusted degrees of freedom.

LSmeans for drug and placebo from this model, denoted \bar{x}_D and \bar{x}_P respectively, the difference in the LSmeans, $\bar{x}_D - \bar{x}_P$, and the associated 2-sided CI and p-value will be taken from the LSmeans statement in PROC MIXED.

Note that for the analysis of these variables on the transformed scale representing velocity rather than time, transformation will be applied to the imputed data x_{ijk} to give the velocity values u_{ijk} used in the analysis model described above. The results from the model will be presented on the transformed scale without back transformation and will be interpreted as estimates of velocity.

Variables with any Class 2 missing data where lower values are worse

For the following variables, the directionality is such that lower values represent a worse outcome:

- 6MWT
- Percent predicted 6MWT
- NSAA
- Muscle strength evaluated by knee extension and elbow flexion as measured by HHM.

If any Class 2 missing data are identified for these variables, the analysis of the variable will be performed as follows:

If x_{ijk} represents the value of the variable to be analysed for subject i randomised to treatment j at time k , then subjects with missing data will be imputed as

Class 1: $x_{ijk} = \bar{x}_{jk}$ where \bar{x}_{jk} is the mean of all non-missing values for the respective measurement at time k across all subjects randomised to treatment j and in the respective concomitant steroid stratum and Group (i.e. Group A, target population or Group B, off-target population).

Class 2: $x_{ijk} = 0$

The exception to this is the NSAA total score which will be derived from imputed item scores as described in Appendix 7.5.4.

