7.5.4 Physical Function as Measured by NSAA

For the purposes of calculating total NSAA score, classification of missing data should be applied as follows:

Class 1 - Either of the following:

- ‘Was assessment attempted?’ = ‘No’ and the reason given is ‘Declined to perform test’ or ‘Other’. In this case, each item score will be imputed using the mode of the non-missing scores for the same item and visit across all subjects randomised to the same treatment and in the same concomitant steroid stratum and Group (i.e. Group A, target population or Group B, off-target population). If there are multiple mode values then the lowest modal value will be used. The total score will be re-derived as the sum of the 17 imputed item scores.
- ‘Was assessment attempted?’ = ‘Yes’ but one or more of the item scores is missing. In this case one of two possible methods will be followed:

- If ≥ 9 out of 17 items have been completed with ≤ 8 missing, then the missing item scores for that subject at that visit will be imputed using the mode of the non-missing item scores for the subject and visit. If there are multiple mode values then the lowest modal value will be used. The total score will be re-derived as the sum of the 17 non-missing and imputed item scores.
- If ≤ 8 out of 17 items have been completed with ≥ 9 missing, then the missing item scores for that subject at that visit will be imputed as zero. The total score will be re-derived as the sum of the 17 non-missing and imputed item scores.

Class 2 - 'Was assessment attempted?' = 'No' and the reason given is 'Unable to physically perform the test'. In this case all item scores and the total score will be imputed to zero.

For the purposes of calculating cumulative number of failed items, NSAA data will first be classified and imputed according to the above rules and the assessment of item failure will then be determined using the values after imputation.

7.5.5 Muscle Strength Evaluated by Knee Extension and Elbow Flexion as Measured by Hand-held Myometry

Class 1 – Either of the following:

- 'Was assessment attempted?' = 'No' and the reason given is 'Declined to perform test' or 'Other'.
- 'Were all 4 elements of the extension/flexion assessment attempted?' = 'No' and the reason given is 'Declined to perform test' or 'Other'. Any missing elements of the test (left/right knee extension or left/right elbow flexion) will be classified as 1.

Class 2 – Either of the following:

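### Imputing in raw units before any velocity or log transformation makes Class 1 velocities too low, gives boys who cannot do the test a positive speed, and leaves Class 2 zeros without a logarithm

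*SAP*

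**What the plan says.** **Order.** SAP 4.4.4.1 gives the general rule, with the velocity conversion and the log as its two examples: "Classification and imputation of missing data will be completed prior to any transformation of the data for analysis". SAP 4.1 repeats it for 4SC velocity (4 divided by the time): "where this conversion is applied following any imputation of missing data as described in Section 4.4.4". SAP 4.2.1.1 and 4.3.1 do the same for rise from floor and the 10 m test. SAP 4.4.4.2 derives velocity from the imputed times and reports the model results on that scale.

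**Class 1 (missing for reasons other than inability).** "Any missing values classified as 1 will be imputed using the mean of all non-missing values for the respective measurement and timepoint". The mean is taken within treatment, steroid stratum and Group.

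**Class 2 (unable).** "Any missing values classified as 2 will be imputed by setting the value to zero or to twice the maximum non-missing value recorded", depending on the direction of the test. For the timed tests the maximum "is the maximum non-missing value recorded for the variable across all subjects, regardless of treatment, stratum or Group" (SAP 4.4.4.2). The same section sets 6MWT, percent-predicted 6MWT and muscle strength to zero. For NSAA, Appendix 7.5.4 says: "In this case all item scores and the total score will be imputed to zero".

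**Log option.** SAP 4.4.2, on the continuous efficacy variables: "The need for a possible log transformation of these variables will be investigated prior to unblinding". The decision rests on residuals from a model with no treatment term. Neither an offset nor a rule for zeros is given.

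**Status.** Under SAP 4.4.2 only the primary and key secondary endpoints at 18 months are formal. Other analyses are supportive, with nominal p-values. SAP Addendum 1 leaves all of this unchanged.

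**The concern.** A mean does not carry through a reciprocal or a logarithm, so a value that is neutral in seconds is not neutral in stairs per second or in log seconds. Three things follow from the stated order.

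1. Every Class 1 velocity lies below the mean velocity of the boys it was built from. The size and sign of the effect on the treatment difference depend on which arm has more missing data.
2. On the time scale some arbitrary ceiling is needed for a boy who cannot climb. On the velocity scale zero is available and needs no assumption. The SAP instead gives him a speed set by the single slowest time in the trial.
3. If a log is chosen for an endpoint whose Class 2 value is zero, the boys who lost the function have no defined outcome. 6MWT, NSAA total and strength belong to the Hochberg family of SAP 4.4.5, so an unplanned choice could enter alpha-controlled analyses.

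**Working it through.** The documents state no figure on this point, so there is none to reproduce.

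**Inputs from the documents.** The imputation rules above. 8% drop-out (SAP 2.5), used as an illustrative Class 1 share. 110 boys randomised 2:1, about 73 and 37. SD 3.094 s (SAP 2.5), which is an SD of change and serves here only as a proxy for the spread of 18-month times.

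**Assumed.** Lognormal times; CV c of 0.3, 0.5 or 0.8; 18-month means of 7 s (placebo) and 6 s (givinostat); maximum times of 10 to 60 s.

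**Step 1: Class 1 velocity.** A simple case: observed times of 2 s and 8 s give an imputed velocity of 4/5 = 0.80, while the mean velocity is (2.00 + 0.50)/2 = 1.25 stairs/s. For lognormal times with mean m, the mean velocity is (4/m)(1 + c²) and the imputed value is 4/m, so the shortfall is c²/(1 + c²):
- c = 0.3: 0.09/1.09 = 8.3%
- c = 0.5: 0.25/1.25 = 20.0%
- c = 0.8: 0.64/1.64 = 39.0%

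With 8% of an arm imputed, its mean is low by 0.08 times these, that is 0.7%, 1.6% and 3.1%. The constant 4 cancels, so the percentages also hold for rise from floor and 10 m.

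**Step 2: Class 2 velocity for 4SC.** 4/(2 × max) = 0.20, 0.10, 0.067 and 0.033 stairs/s for a maximum of 10, 20, 30 and 60 s.

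**Step 3: treatment difference in mean 4SC velocity.** Simulated with 37 and 73 boys over 3,000 replicates, ignoring strata and covariates. The comparison imputes Class 1 as the mean observed velocity and sets Class 2 to 0.

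| Class 1, placebo/givinostat | Class 2, placebo/givinostat | SAP order | Imputed as velocity | SAP order relative to comparison |
|---|---|---|---|---|
| 8%/8% | none | 0.1539 | 0.1593 | −3.4% |
| 4%/12% | none | 0.1429 | 0.1595 | −10.4% |
| 12%/4% | none | 0.1669 | 0.1608 | +3.8% |
| 8%/8% | 8%/3% | 0.1790 | 0.1899 | −5.7% |

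Hand check of the second row:
- Placebo: c² = (3.094/7)² = 0.1954, mean velocity (4/7)(1.1954) = 0.6831, shortfall 16.3%. With 4% imputed: 0.6831 × (1 − 0.04 × 0.163) = 0.6786.
- Givinostat: c² = (3.094/6)² = 0.2659, mean velocity (4/6)(1.2659) = 0.8439, shortfall 21.0%. With 12% imputed: 0.8439 × (1 − 0.12 × 0.210) = 0.8226.
- Difference: 0.8226 − 0.6786 = 0.1440, against 0.8439 − 0.6831 = 0.1608. This is 10.4% lower and agrees with the simulation.

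**Step 4: log scale.** A Class 1 time equals the arithmetic mean, which exceeds the geometric mean by √(1 + c²) − 1 = 4.4%, 11.8% and 28.1% for the three CVs. This would apply to 4SC too if 4SC were logged. For Class 2 zeros log(0) is undefined. With an improvised offset k, a fall from an assumed 400 m to 0 is log(k/(400 + k)) = −5.99, −8.29 and −10.60 for k = 1, 0.1 and 0.01. Divided by 37, one such boy moves the placebo mean log change by −0.16, −0.22 or −0.29, depending only on k.

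**The case against.** The velocity analyses are supportive with nominal p-values, so an error in them changes no formal conclusion. In three of the four scenarios the SAP order understates the drug effect, and with equal missingness the shift is small. Doubling the maximum time gives exactly half the slowest observed velocity, so boys who cannot climb still rank last, and using one imputed dataset for both scales is a coherent choice. The log is conditional: zeros would probably come to light when residuals are examined before unblinding. A 6MWT zero also needs a specific record under Appendix 7.5.3 (performed, stopped prematurely, duration and distance both blank). A test marked as not performed is Class 1.

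All of this stands as a limit on size. It does not make the stated order correct: the results are to be read as estimates of velocity, and the SAP is silent on what to do once a zero is found.

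Two stronger readings are tempting. A reader might infer that velocity is the main check on the primary result. SAP 4.1 presents it only as an additional assessment, and the missing-data check named for the primary is the tipping-point analysis in SAP 4.4.4.3. A reader might also infer that the SAP takes logs of change scores, which fail for any non-positive change. SAP 4.4.4.2 imputes observed values before forming the change and converts observed times to velocity, and SAP 4.4.4.1 lists the log beside that conversion. The wording is loose, but logging the measured values is the more natural reading.

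**Conclusion.** The point holds and is worth correcting, with limited reach. For velocity the defect follows directly from the stated order whenever Class 1 or Class 2 data occur. Each Class 1 value is too low by 8% to 39% over the assumed CVs. The treatment difference moves by about 3% with equal Class 1 missingness and by roughly 4% to 10% in the two unequal cases, in a direction set by which arm has more missing data. These sizes rest on lognormal times, the assumed means, the proxy SD and the assumed missingness rates. The direction of the Class 1 bias needs only that times vary.

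The log problem is conditional on a blinded decision and on Class 2 zeros occurring. If both happen, formal analyses of 6MWT, strength or NSAA total would lose those boys or depend on an unplanned offset, as would the exploratory percent-predicted 6MWT. The documents do not show that boys will in fact be dropped, only that no rule prevents it. NSAA Class 1 values are imputed from modes, so the mean-imputation argument does not apply there. The untransformed primary 4SC analysis is not affected.

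**What to change.** Amend SAP 4.4.4.1, 4.4.4.2 and 4.4.2, and the matching sentences in 4.1, 4.2.1.1 and 4.3.1:

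- Impute Class 1 values on the scale analysed, as the mean of observed velocities or of observed log values in the same treatment, stratum and Group cell.
- Set velocity to 0 for Class 2.
- Limit the log option to strictly positive endpoints (the timed tests and VL MFF). Define the outcome as log(18-month/baseline) with log baseline as covariate, and report the effect as a ratio. This also settles what is being logged.
- Keep 6MWT, percent-predicted 6MWT, NSAA and strength untransformed.

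The cost is a few SAP sentences and a change in programming order. No new data are needed. The log rule should be fixed before unblinding, since SAP 4.4.2 places the choice there.

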4.4.4.2 Analysis

Once classified and imputed, the following procedures will be applied for the analysis of endpoints where there are missing data with imputation. The approach will be dependent on the class(es) of missing data present and also the directionality of the test where Class 2 missing data are present. Any analysis of binary or time to event variables with missing data, or the cumulative loss of function on the NSAA, will use the appropriate procedure described in Section 4.4.2, following any classification and imputation per the methods above. Thus, the below procedures apply only to the continuous variables.

Note that where the endpoint to be analysed is a change from baseline, any imputation (per the following procedures) will be applied to the observed values prior to finding the corresponding change from baseline.

Variables with only Class 1 missing data

For the following variables, only Class 1 missing data will be applicable:

- VL MFF determined by MRS
- PODCI standardised scores for each subscale and the global function scale, as completed by the parent and the subject
- Fat fraction in 5 thigh muscles as determined by MRI
- Cross-sectional area of 5 thigh muscles as determined by MRI
- Any other variable where all missing values have been classified as 1 and no Class 2 missing values have been identified.

Any missing values will be imputed as per the rules for Class 1 missing data and the applicable analysis will be performed as described in Section 4.4.2 and Sections 4.1 to 4.3.10 as relevant to the respective variable.

Variables with any Class 2 missing data where higher values are worse

For the following variables, the directionality is such that higher values represent a worse outcome:

- 4SC
- Time to rise from the floor
- Time to run/walk 10 metres

If any Class 2 missing data are identified for these variables, the analysis of the variable will be performed as follows:

If x_{ijk} represents the value of the variable to be analysed for subject i randomised to treatment j at time k , then missing data will be imputed as

Class 1: $x_{ijk} = \bar{x}_{jk}$ where \bar{x}_{jk} is the mean of all non-missing values for the respective measurement at time k across all subjects randomised to treatment j and in the respective concomitant steroid stratum and Group (i.e. Group A, target population or Group B, off-target population).

Class 2: $x_{ijk} = 2 \times \text{Max}(x)$ where $\text{Max}(x)$ is the maximum non-missing value recorded for the variable across all subjects, regardless of treatment, stratum or Group.

Following the assignment of imputed values, the data x_{ijk} will be analysed as described in Section 4.4.2 and Sections 4.1 to 4.3.10, as relevant to the respective variable using PROC MIXED, ensuring that reference levels are stated for all class variables so that difference in LSmeans is calculated as givinostat-placebo. F-tests from PROC MIXED will be based on Kenward-Roger's adjusted degrees of freedom.

LSmeans for drug and placebo from this model, denoted \bar{x}_D and \bar{x}_P respectively, the difference in the LSmeans, $\bar{x}_D - \bar{x}_P$, and the associated 2-sided CI and p-value will be taken from the LSmeans statement in PROC MIXED.

Note that for the analysis of these variables on the transformed scale representing velocity rather than time, transformation will be applied to the imputed data x_{ijk} to give the velocity values u_{ijk} used in the analysis model described above. The results from the model will be presented on the transformed scale without back transformation and will be interpreted as estimates of velocity.

Variables with any Class 2 missing data where lower values are worse

For the following variables, the directionality is such that lower values represent a worse outcome:

- 6MWT
- Percent predicted 6MWT
- NSAA
- Muscle strength evaluated by knee extension and elbow flexion as measured by HHM.

If any Class 2 missing data are identified for these variables, the analysis of the variable will be performed as follows:

If x_{ijk} represents the value of the variable to be analysed for subject i randomised to treatment j at time k , then subjects with missing data will be imputed as

Class 1: $x_{ijk} = \bar{x}_{jk}$ where \bar{x}_{jk} is the mean of all non-missing values for the respective measurement at time k across all subjects randomised to treatment j and in the respective concomitant steroid stratum and Group (i.e. Group A, target population or Group B, off-target population).

Class 2: $x_{ijk} = 0$

The exception to this is the NSAA total score which will be derived from imputed item scores as described in Appendix 7.5.4.

Following the assignment of imputed values, these variables will be analysed as described in Section 4.4.2 and Sections 4.1 to 4.3.10, as relevant to the respective variable, using the same PROC MIXED approach as detailed above.

